9.3 POPULATIONS FOR ANALYSES

Data analyses will adhere to the intention-to-treat principle, allowing 12-months grace period to implement practice changes. The primary analysis will compare the overall proportion of eligible preteens who initiated and completed HPV vaccination in the intervention and control practices at 24 months, using Year 2 measurements for vaccine use. Maintenance of change will be assessed using Year 3 measurements.

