1 PROTOCOL SUMMARY

1.1 SYNOPSIS

Title:	Randomized Controlled Trial to Evaluate an Implementation Strategy to Increase Optimal Use of HPV Vaccine in Primary Care		
Grant Number:	R01CA2356515-01A1		
Study Description:	We will complete a cluster-randomized trial to evaluate the effectiveness of a multi-component implementation strategy (the intervention) to increase use of the HPV vaccine according to CDC guidelines. Twenty community pediatric practices will be randomly assigned to the intervention or wait-list control condition.		
Objectives*:			
	Primary Objective:	Compare, at 24 months, the proportion of eligible preteens who receive 1st dose (primary endpoint) and 2nd dose (secondary endpoint) of HPV vaccine before their 13th birthday in practices that receive the intervention with practices in the wait-list control group.	
	Secondary Objectives:	Compare these outcomes at 36 months to assess the sustainability of intervention benefit.	
		Determine whether the intervention effect on vaccination outcomes is mediated by providers' increased belief in their capabilities to provide on-time HPV vaccination (primary outcome) and by their increased use of a presumptive, announcement approach to recommend HPV vaccine (secondary outcome)	
		Explore if the intervention effect on vaccination outcomes is mediated by the degree of practice change as measured on an 18-item HPV vaccine delivery score.	
		Assess the implementation fidelity, the acceptability and appropriateness of the intervention for providers, parental satisfaction with care, and cost.	

Endpoints*:	Primary Endpoint: The proportion of eligible preteens who receive the 1st dose of HPV vaccine before their 13th birthday at 24 months post randomization. The proportion of eligible preteens who receive the 2nd dose of HPV vaccine before their 13th birthday at 24 months post randomization.
Secondary Endpoint:	The proportion of eligible preteens who receive the 1st dose of HPV vaccine before their 13th birthday at 36 months post randomization.
	The proportion of eligible preteens who receive the 2nd dose of HPV vaccine before their 13th birthday at 36 months post randomization.
Study Population:	Approximately 120 Community based pediatric primary care providers in the St. Louis metropolitan area , who work in the 20 participating practices
Phase* or Stage:	3 (Low-risk behavioral intervention)
Description of Sites/Facilities Enrolling Participants:	The study will be conducted at Washington University

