9 STATISTICAL CONSIDERATIONS

9.1 STATISTICAL HYPOTHESES

- Primary Efficacy Endpoint(s):

We hypothesize that the 2-year intervention will increase the percentage of preteens who receive HPV vaccine before their 13th birthday by at least 13 percentage points at 24 months compared to control, and benefits will be sustained at 36 months.

Alternatively, our null hypothesis is that there will be no difference in HPV vaccine use between the intervention and control groups.

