9.2 SAMPLE SIZE DETERMINATIONS

AIM 1: We will use a cluster randomized design. Study outcomes will be measured at the level of the patient using a cross-sectional design. The sample size determination is based on the primary outcome - initiation of HPV vaccination by age 13. Effectiveness is derived from the difference in the proportion of eligible preteens in the intervention and control groups 24 months after the intervention, and long-term maintenance is derived from the difference in these measures 36 months after intervention. In the control group, national data suggest the baseline vaccine initiation proportion should be 0.4. We expect the vaccine initiation proportion in the control group in this age group will not change over time, and intervention group will have a similar baseline initiation rate to the control group, but will increase by at least 0.13 by 24 months. Thus, the hypothesis to test is $H_0: p=0.4$ vs. $H_1: p=0.53$.

Our study has a three level hierarchical structure: children are clustered within providers which are clustered within practices. Thus, there exists correlations for children seen by the same provider, as well as providers working in the same practice. We use random effects to capture the intra-class correlation at the provider and the practice levels. From our preliminary data, the estimate for random effect variance at the practice level is very close to 0, and that at the provider level is 0.75² (corresponding to an ICC of 0.15). This suggests very little heterogeneity at the practice level, but significant heterogeneity at the provider level. Since there is no ready-to-use software for power calculation for clustered trial in the three level hierarchical structure, we conduct the power calculation by simulation.

In the simulation study, we set $\sigma_a^2 = .01$ for the random effect at the practice level and $\sigma_b^2 = .75^2$ for the random effect at the provider level. We choose the value of β so that the proportion of HPV vaccine rate is 0.4 for control and 0.53 for the intervention. We assume there are 4 physicians in each practice, each physician sees 30 children, resulting a total of 120 patients in each practice. The sample size to calculate is the number of practices. The simulation study is carried out in R, using function *glmer()* in the *mle4* package for estimation of the generalized linear mixed effects model (1) below.

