9.4 STATISTICAL ANALYSES

9.4.1 GENERAL APPROACH

All main data analyses will adhere to the intention-to-treat principle, and a probability of $P < 0.05$ will be used to establish statistical significance (2-tailed test). Before we perform complicated statistical modeling, we will conduct exploratory data analysis. For continuous variables, we will examine their distribution, and summarize them with mean/standard deviation if data are reasonably normally

distributed, or with median/interquartile range if data are skewed. We will use Rosner's outlier detection routine. Categorical data will be summarized by proportions. Simple comparison of continuous variables between intervention and control group will be performed using two sample t test or non-parametric Wilcoxon test. Simple comparison of categorical variable will be performed using chi-square test or fisher exact test where appropriate.

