9.4.2 ANALYSIS OF THE PRIMARY ENDPOINT(S)

Data analyses will adhere to the intention-to-treat principle, allowing 12-months grace period to implement practice changes. The primary analysis will compare the overall proportion of eligible preteens who initiated and completed HPV vaccination in the intervention and control practices at 24 months, using Year 2 measurements for vaccine use. Maintenance of change will be assessed using Year 3 measurements. The analytic approach is to use a multi-level random effects logistic model to account for the hierarchical structure: children clustered within providers clustered within practices.

Define by y_{ijk} as the binary variable of HPV vaccine for the k th child of provider j of practice i . There are 3 hierarchical levels: children clustered within providers clustered within practices. We use random effects to capture the intra-class correlation at the provider and the practice levels. We assume a multi-level random effects logistic model (a generalized linear mixed model):

$$\text{logit } P(y_{ijk}=1) = \beta_0 + trt_{ijk}\beta_1 + a_i + b_{ij} \quad (1)$$

[figure not shown]
where trt_{ijk} is the treatment indicator for practice i , and β_1 is the treatment effect. We use random effects a_i and b_{ij} to describe heterogeneity in the practice level and provider level, and assume $a_i \sim N(0, \sigma_a^2)$ and $b_{ij} \sim N(0, \sigma_b^2)$ are independent. The practice level random intercept is used to accommodate extra-variation in outcome measurements due to clustering of providers in a practice, and the provider level random intercept is used to accommodate extra-variation in outcome measurements due to clustering of individual patients within a provider.

As secondary analysis, we can add other covariates in the model, e.g., gender, category of practice (urban vs. rural), vaccine rate at baseline for a provider or practice, etc. Interaction of treatment and these covariates can be included in the model to study the moderating effect of these risk factors. The interaction of random effects (both at the practice and provider levels) and covariates can be added in the model as well.

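### Sustainability is assessed only by the 36-month arm difference; the 24- and 36-month effects are never compared and no criterion for 'sustained' is given

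*Combined protocol and SAP*

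**What the plan says.** The first hypothesis (4.1 and 9.1) has two parts: a gain of at least 13 points at 24 months, and that "benefits will be sustained at 36 months". The second part is taken up in four places:

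- Synopsis, secondary objective: "Compare these outcomes at 36 months to assess the sustainability of intervention benefit".
- 9.2: "long-term maintenance is derived from the difference in these measures 36 months after intervention".
- 9.3 and again 9.4.2: "Maintenance of change will be assessed using Year 3 measurements".
- 9.1, the only null stated: "our null hypothesis is that there will be no difference in HPV vaccine use between the intervention and control groups". Section 9.4.1 sets two-tailed P < 0.05 for all main analyses.

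Model (1) in 9.4.2 has an intercept, one treatment coefficient and random intercepts for practice and provider. It has no year term and no treatment-by-year term. The optional covariates and interactions in 9.4.2, 9.4.7 and 9.4.9 name gender, practice category and baseline vaccination rate, not measurement year. No section contrasts the two years, sets a retained fraction or defines 'sustained'.

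**The concern.** In ordinary use, 'sustained' means that the benefit seen at 24 months is still there, at about its former size, at 36 months. The planned evidence answers a narrower question: does any arm difference remain in Year 3? A significant Year 3 result is compatible with a sizeable loss. A non-significant one after a significant Year 2 result does not show loss, because the change itself has not been estimated.

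The conclusion carries weight in this trial. Section 4.2 gives the 3-year follow-up needed to assess sustained change as the reason a stepped wedge design was ruled out. Section 2.1 names the lack of evidence of sustained benefit as a gap in earlier work.

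**Working it through.** **Inputs from the documents.** From 9.2: "the proportion of HPV vaccine rate is 0.4 for control and 0.53 for the intervention" (a 13-point effect); practice variance 0.01 and provider variance 0.75² = 0.5625 on the logit scale; 10 practices per arm; originally 4 providers per practice and 30 children per provider, now 95 providers (47.5 per arm on average) and 60 charts each.

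**Assumed.** Control rate 0.40 in both years (9.2 also assumes no change in controls), rates read as population averages, equal average cluster sizes in the closed form, and no loss of practices or providers.

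**Variance components on the probability scale** (integrating the logistic-normal model):

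| Rate | Practice | Provider | Child |
|---|---|---|---|
| 0.40 | 0.00046 | 0.0260 | 0.2135 |
| 0.53 | 0.00049 | 0.0277 | 0.2209 |

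Variance of an arm's proportion = practice/10 + provider/(providers per arm) + child/(charts per arm).

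**1. The plan's own figure.** With 40 providers and 1,200 charts per arm:
- Control: 0.000046 + 0.000650 + 0.000178 = 0.000874.
- Intervention: 0.000049 + 0.000692 + 0.000184 = 0.000925.
- SE = √0.001799 = 0.0424.
- Power = Φ(0.13/0.0424 − 1.96) = Φ(1.105) = 0.865.

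Simulating the three-level logistic model gives 0.863. The plan's power of over 0.80 reproduces. If the rates are instead read as conditional on zero random effects, power is 0.775 by closed form and 0.793 by simulation.

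**2. The 36-month difference at current size.** With 47.5 providers and 2,850 charts per arm:
- Control: 0.000046 + 0.000548 + 0.000075 = 0.000668 (from unrounded terms).
- Intervention: 0.000049 + 0.000583 + 0.000078 = 0.000709 (likewise).
- SE = √0.001377 = 0.0371, or 3.71 points.
- Smallest significant difference: 1.96 × 3.71 = 7.3 points (7.3/13 = 56%), or with t on 20 − 2 = 18 df, 2.101 × 3.71 = 7.8 points (7.8/13 = 60%).

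**3. Probability that the 36-month difference is significant, by true effect.**

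| Method | All 13 points kept | A third lost (8.7) | Half lost (6.5) |
|---|---|---|---|
| Closed form, z | 0.94 | 0.65 | 0.42 |
| Closed form, t on 18 df | 0.91 | 0.60 | 0.38 |
| Three-level logistic model simulated, Wald z | – | 0.66 | 0.47 |
| Weighted practice means simulated, t on 18 df | 0.88 | – | 0.33 |

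For example, with half lost and z: Φ(6.5/3.71 − 1.96) = Φ(−0.21) = 0.42. The last row assumes an uneven split of 2 to 8 providers per practice, which gives an SE of about 3.9 points and a threshold of about 8.3 points. A dash means not run.

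**4. Precision of the missing contrast.** Let ρ be the correlation of provider and practice effects between Years 2 and 3. The documents give no value. Summed over arms, the cluster part of the variance in step 2 is 0.001225 and the child part is 0.000152. Then Var(change) ≈ 2(1 − ρ) × 0.001225 + 2 × 0.000152.

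| Assumed ρ | SE of change, points | 95% CI half-width (z), points | Power to detect a halving (t on 18 df) |
|---|---|---|---|
| 1.0 | 1.7 | 3.4 | 0.94 |
| 0.8 | 2.8 | 5.5 | 0.59 |
| 0.5 | 3.9 | 7.7 | 0.35 |

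**The case against.** The plan defines its own target. The Synopsis and 9.2 equate sustainability with the arm difference at 36 months. Asking whether intervention practices still outperform controls a year after facilitation ends is a coherent question. Both arm differences will be available, so a fall from 13 to 8 points would be visible. This justifies keeping the 36-month comparison. It does not supply the contrast: 8.1 samples each participating provider's records in every period, so the two estimates are correlated, and two separate intervals do not give an interval for the change.

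Three stronger readings are tempting, and the documents do not support them.

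- *The plan will declare benefit sustained if P < 0.05 at 36 months.* No section says so. That rule can only be inferred by joining the general null in 9.1, the definition in 9.2 and the threshold in 9.4.1. What can be said is that no criterion is stated and no other threshold appears.
- *An observed halving would pass.* A fall from exactly 13 to 6.5 points gives 6.5/3.71 = 1.75, below 1.96, so it would not be significant. The halving figures apply to the true effect and are probabilities.
- *The test is wrong in both directions.* Missing a fully kept effect in 6 to 12% of trials is ordinary type II error, with power above the plan's 0.80.

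It is also fair that the added contrast may be imprecise, and that pairing helps only for providers present in both audits. Section 7.2 lets providers withdraw, and turnover is not described.

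**Conclusion.** The point holds as a cheap improvement to a secondary objective. The 24-month primary analysis is unaffected. The plan neither compares the 24- and 36-month effects nor says what 'sustained' requires, so a significant 36-month result would support persistence of some benefit and no more.

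The sizes in steps 2 and 3 rest on the plan's planning values, the current 95 providers at 60 charts each, and the assumptions listed. The spread between methods is real: only one row of step 3 fits the plan's own model, so no single figure should be taken as the plan's operating characteristic. The precision of the change depends on a year-to-year correlation that the documents do not give.

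**What to change.** In 9.3 and 9.4.2, keep the 36-month comparison and add:

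1. A joint model of Year 2 and Year 3 records with arm, year and arm-by-year terms, and practice and provider random effects that may differ by year.
2. Two reported quantities, each in percentage points with a cluster-appropriate 95% CI: the 36-month arm difference, and the change in arm difference from 24 to 36 months.
3. Rules of interpretation. A significant 36-month difference alone shows that some benefit persists. 'Sustained' is judged from the estimate and CI of the change, read with the 36-month difference. A non-significant change is not evidence of maintenance.

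The cost is SAP wording and one further model on records already planned for collection, with no new data or participants. The downside is that the conclusion may be less definite, since the interval for the change could be wide if provider performance shifts between years or providers leave between audits.

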9.4 STATISTICAL ANALYSES

9.4.1 GENERAL APPROACH

All main data analyses will adhere to the intention-to-treat principle, and a probability of $P < 0.05$ will be used to establish statistical significance (2-tailed test). Before we perform complicated statistical modeling, we will conduct exploratory data analysis. For continuous variables, we will examine their distribution, and summarize them with mean/standard deviation if data are reasonably normally

distributed, or with median/interquartile range if data are skewed. We will use Rosner's outlier detection routine. Categorical data will be summarized by proportions. Simple comparison of continuous variables between intervention and control group will be performed using two sample t test or non-parametric Wilcoxon test. Simple comparison of categorical variable will be performed using chi-square test or fisher exact test where appropriate.

9.4.2 ANALYSIS OF THE PRIMARY ENDPOINT(S)

Data analyses will adhere to the intention-to-treat principle, allowing 12-months grace period to implement practice changes. The primary analysis will compare the overall proportion of eligible preteens who initiated and completed HPV vaccination in the intervention and control practices at 24 months, using Year 2 measurements for vaccine use. Maintenance of change will be assessed using Year 3 measurements. The analytic approach is to use a multi-level random effects logistic model to account for the hierarchical structure: children clustered within providers clustered within practices.

Define by y_{ijk} as the binary variable of HPV vaccine for the k th child of provider j of practice i . There are 3 hierarchical levels: children clustered within providers clustered within practices. We use random effects to capture the intra-class correlation at the provider and the practice levels. We assume a multi-level random effects logistic model (a generalized linear mixed model):

$$\text{logit } P(y_{ijk}=1) = \beta_0 + trt_{ijk}\beta_1 + a_i + b_{ij} \quad (1)$$

[figure not shown]
where trt_{ijk} is the treatment indicator for practice i , and β_1 is the treatment effect. We use random effects a_i and b_{ij} to describe heterogeneity in the practice level and provider level, and assume $a_i \sim N(0, \sigma_a^2)$ and $b_{ij} \sim N(0, \sigma_b^2)$ are independent. The practice level random intercept is used to accommodate extra-variation in outcome measurements due to clustering of providers in a practice, and the provider level random intercept is used to accommodate extra-variation in outcome measurements due to clustering of individual patients within a provider.

As secondary analysis, we can add other covariates in the model, e.g., gender, category of practice (urban vs. rural), vaccine rate at baseline for a provider or practice, etc. Interaction of treatment and these covariates can be included in the model to study the moderating effect of these risk factors. The interaction of random effects (both at the practice and provider levels) and covariates can be added in the model as well.

Missing Data: As in any other study, we expect some missing data in our study. If missing data affects the validity of statistical inference, we will follow Little and Rubin to deal with this problem.⁷⁸ If the assumption of "missing at random" holds, this approach will avoid bias and preserves the study power. Specifically, multiple imputed completed datasets, say 5, will be generated through parametric (or nonparametric) Bayesian models. For each imputed dataset, the standard statistical method is applied to obtain the parameter estimates with the estimated variance and covariance. Then, these parameter estimates with their variance and covariance estimates can be used to generate overall parameter estimates and their standard errors.

